5.2.6.1.2 Serious adverse event

A serious adverse event (SAE) is defined as any AE which fulfils at least one of the following criteria:

- Results in death
- Is life-threatening, which refers to an event in which the patient was at risk of death at the time of the event; it does not refer to an event that hypothetically might have caused death if more severe
- Requires inpatient hospitalisation
- Requires prolongation of existing hospitalisation
- Results in persistent or significant disability or incapacity
- Is a congenital anomaly/birth defect
- Is deemed serious for any other reason if it is an important medical event when based upon appropriate medical judgment which may jeopardise the patient and may require medical or surgical intervention to prevent one of the other outcomes listed in the above definitions. Examples of such events are intensive treatment in an emergency room or at home for allergic bronchospasm, blood dyscrasias or convulsions that do not result in hospitalisation or development of dependency or abuse

5.2.6.1.3 AEs considered ‘Always Serious’

Cancers of new histology and exacerbations of existing cancer must be classified as a serious event regardless of the time since discontinuation of the trial medication and must be reported as described in [5.2.6.2](#), subsections ‘AE Collection’ and ‘**AE reporting to sponsor and timelines**’.

In accordance with the European Medicines Agency initiative on Important Medical Events, Boehringer Ingelheim has set up a list of further AEs, which, by their nature, can always be considered to be ‘serious’ even though they may not have met the criteria of an SAE as defined above.

The latest list of ‘Always Serious AEs’ can be found in the eDC system, an electronic data capture system which allows the entry of trial data at the trial site. These events should always be reported as SAEs as described above.

5.2.6.1.4 Adverse events of special interest

The term adverse events of special interest (AESI) relates to any specific AE that has been identified at the project level as being of particular concern for prospective safety monitoring and safety assessment within this trial, e.g. the potential for AEs based on knowledge from other compounds in the same class. AESIs need to be reported to the sponsor’s Pharmacovigilance Department within the same timeframe that applies to SAEs, please see Section [5.2.6.2.2](#).

The following are considered as AESIs:

- Hepatic injury

A hepatic injury is defined by the following alterations of hepatic laboratory parameters:

- o An elevation of AST (aspartate transaminase) and/or ALT (alanine transaminase) ≥ 3 -fold ULN combined with an elevation of total bilirubin ≥ 2 -fold ULN measured in the same blood sample, or
- o Aminotransferase (ALT, and/or AST) elevations ≥ 10 fold ULN

These lab findings constitute a hepatic injury alert and the subjects showing these lab abnormalities need to be followed up according to the 'DILI checklist' provided in the ISF. In case of clinical symptoms of hepatic injury (icterus, unexplained encephalopathy, unexplained coagulopathy, right upper quadrant abdominal pain, etc.) without lab results (ALT, AST, total bilirubin) available, the Investigator should make sure that these parameters are analysed, if necessary in an unscheduled blood test. Should the results meet the criteria of hepatic injury alert, the procedures described in the DILI checklist should be followed.

5.2.6.1.5 Intensity (severity) of AEs

The intensity (severity) of the AE should be judged based on the following:

Mild: Awareness of sign(s) or symptom(s) that is/are easily tolerated

Moderate: Sufficient discomfort to cause interference with usual activity

Severe: Incapacitating or causing inability to work or to perform usual activities

5.2.6.1.6 Causal relationship of AEs

Medical judgment should be used to determine the relationship, considering all relevant factors, including pattern of reaction, temporal relationship, de-challenge or re-challenge, confounding factors such as concomitant medication, concomitant diseases and relevant history.

Arguments that may suggest that there is a reasonable possibility of a causal relationship could be:

- The event is consistent with the known pharmacology of the drug
- The event is known to be caused by or attributed to the drug class
- A plausible time to onset of the event relative to the time of drug exposure
- Evidence that the event is reproducible when the drug is re-introduced
- No medically sound alternative aetiologies that could explain the event (e.g. pre-existing or concomitant diseases, or co-medications)
- The event is typically drug-related and infrequent in the general population not exposed to drugs (e.g. Stevens-Johnson syndrome)
- An indication of dose-response (i.e. greater effect size if the dose is increased, smaller effect size if dose is reduced)

Proprietary confidential information © 2020 Boehringer Ingelheim International GmbH or one or more of its affiliated companies

Arguments that may suggest that there is no reasonable possibility of a causal relationship could be:

- No plausible time to onset of the event relative to the time of drug exposure is evident (e.g. pre-treatment cases, diagnosis of cancer or chronic disease within days / weeks of drug administration; an allergic reaction weeks after discontinuation of the drug concerned)
- Continuation of the event despite the withdrawal of the medication, taking into account the pharmacological properties of the compound (e.g. after 5 half-lives). Of note, this criterion may not be applicable to events whose time course is prolonged despite removing the original trigger
- Additional arguments amongst those stated before, like alternative explanation (e.g. situations where other drugs or underlying diseases appear to provide a more likely explanation for the observed event than the drug concerned)
- Disappearance of the event even though the trial drug treatment continues or remains unchanged

5.2.6.2 Adverse event collection and reporting

5.2.6.2.1 AE collection

Upon enrolment into a trial, the subject's baseline condition is assessed (for instance, by documentation of medical history/concomitant diagnoses), and relevant changes from baseline are noted subsequently.

Subjects will be required to report spontaneously any AEs as well as the time of onset, end time, and intensity of these events. In addition, each subject will be regularly assessed by the medical staff throughout the clinical trial and whenever the investigator deems necessary. As a minimum, subjects will be questioned for AEs (and concomitant therapies) at the time points indicated in the [Flow Chart](#). Assessment will be made using non-specific questions such as 'How do you feel?'. Specific questions will be asked wherever necessary in order to more precisely describe an AE.

A carefully written record of all AEs shall be kept by the investigator in charge of the trial. Records of AEs shall include data on the time of onset, end time, intensity of the event, and any treatment or action required for the event and its outcome.

The following must be collected and documented on the appropriate CRF(s) by the investigator:

- From signing the informed consent onwards until an individual subject's end of trial:
 - All AEs (serious and non-serious) and all AESIs
 - The only exception to this rule are AEs (serious and non-serious) and AESIs in Phase I trials in healthy volunteers, when subjects discontinue from the trial due to screening failures prior to administration of any trial medication. In these cases, the subjects' data must be collected at trial site but will not be entered in the CRF or trial database and will not be reported in the CTR.

Proprietary confidential information © 2020 Boehringer Ingelheim International GmbH or one or more of its affiliated companies

- After the individual subject's end of trial:
 - The investigator does not need to actively monitor the subject for AEs but should only report any occurrence of cancer and related SAEs and related AESIs of which the investigator may become aware of by any means of communication, e.g. phone call. Those AEs should, however, not be reported in the CRF.

5.2.6.2.2 AE reporting to the sponsor and timelines

The Investigator must report SAEs, AESIs, and non-serious AEs which are relevant for the reported SAE or AESI, on the BI SAE form via fax immediately (within 24 hours) to the sponsor's unique entry point (country specific contact details will be provided in the ISF). The same timeline applies if follow-up information becomes available. In specific occasions the Investigator could inform the sponsor upfront via telephone. This does not replace the requirement to complete and fax the BI SAE form.

With receipt of any further information to these events, a follow-up SAE form has to be provided. For follow-up information, the same rules and timeline apply as for initial information.

5.2.6.2.3 Information required

All (S)AEs, including those persisting after the individual subject's end of trial, must be followed up until they have resolved, have been sufficiently assessed as 'chronic' or 'stable', or no further information can be obtained.

5.2.6.2.4 Pregnancy

Once the male subject has been enrolled in the clinical trial and has taken trial medication, and if a partner of the male trial participant becomes pregnant, the investigator must report any drug exposure during pregnancy in a partner of the male trial participant immediately (within 24 hours) by means of Part A of the Pregnancy Monitoring Form to the sponsor's unique entry point, after a written consent of the pregnant partner.

The outcome of the pregnancy associated with the drug exposure during pregnancy must be followed up and reported to the sponsor's unique entry point on the Pregnancy Monitoring Form for Clinical Trials (Part B).

The ISF will contain the Pregnancy Monitoring Form for Clinical Trials (Part A and Part B) as well as non-trial specific information and consent for the pregnant partner.

As pregnancy itself is not to be reported as an AE, in the absence of an accompanying SAE and/or AESI, only the Pregnancy Monitoring Form for Clinical Trials and not the SAE form is to be completed. If there is an SAE and/or AESI associated with the pregnancy, an SAE form must be completed in addition.

5.2.6.3 Collection and reporting of the adverse event headache

If the subject reports headaches during the treatment period the following information and data should be collected daily until the headache is resolved:

Proprietary confidential information © 2020 Boehringer Ingelheim International GmbH or one or more of its affiliated companies

- Onset after medication intake (hhh:min)
- Headache severity on a Numeric Ranking Scale (NRS) ranging from 0 – 10
- Quality of headache (New type of headache vs. similar to previous experienced episodes of known headaches)
- Headache characteristics (pressing or tightening vs. burning vs. pulsating vs. aggravated by routine physical activity (such as walking or climbing stairs)
- Location (all of the following that apply: unilateral, bilateral, holocephal, frontal, temporal, occipital, facial)
- Any accompanying symptoms like (all of the following that apply: nausea and/or vomiting, photophobia, phonophobia, lacrimation, other)
- If Headache is resolved: Overall duration of headache episode (start time and end time)

5.3 DRUG CONCENTRATION MEASUREMENTS AND PHARMACOKINETICS

5.3.1 Assessment of pharmacokinetics

For the assessment of pharmacokinetics, blood and urine samples will be collected at the time points/time intervals indicated in the [Flow Chart](#). The actual sampling times will be recorded and used for determination of pharmacokinetic parameters.

5.3.2 Methods of sample collection for Part 1

5.3.2.1 Sampling of whole blood and plasma

Whole blood and plasma will be collected at time points shown in the [Flow Chart](#):

- To determine [¹⁴C]-radioactivity concentrations in whole blood and plasma
- To determine concentrations of BI 1358894 in plasma
- To identify metabolites of BI 1358894 in plasma

Blood for pharmacokinetics of BI 1358894 and for quantification of its metabolites will be taken from an antecubital or forearm vein into a K2-EDTA (dipotassium ethylenediaminetetraacetic acid)- anticoagulant blood drawing tube at the times indicated in the [Flow Chart](#). Withdrawal of blood will be done via an indwelling cannula or by direct venepuncture.

For a detailed description of blood sampling, sample volume, sample handling, sample preparation, sample storage, tube labelling and sample shipment, refer to the laboratory manual.

[figure not shown]
Premature stopping of blood sampling

In case [¹⁴C]-radioactivity in plasma samples is not detectable (<LLOQ 30 dpm/mL) at two consecutive time points for a subject, blood sampling can be stopped for this subject.

Proprietary confidential information © 2020 Boehringer Ingelheim International GmbH or one or more of its affiliated companies

However, all samples until 24 h after the last drug administration have to be taken.

For a detailed description of blood sampling, sample volume, sample handling, sample preparation, sample storage, tube labelling and sample shipment, refer to the laboratory manual.

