	50	1181:00	13:00	Discharge from trial site ¹⁰			▼		x	
3	16-50			End of trial (EOT) examination ^{7,12,15}	C ¹⁷				x	x

A, B & C: safety laboratory sets (see Table 5.2.3:1)

1. Screening includes subject information, informed consent, physical examination, check of vital signs, ECG, safety laboratory (including drug and virus screening), demographics (including determination of body height and weight, smoking status and alcohol history), relevant medical history, concomitant therapy and review of inclusion/exclusion criteria, neurological examination and suicidality assessment (C-SSRS).
2. Pharmacokinetics (PK): BI 1358894 and metabolites in plasma; [¹⁴C]-radioactivity in whole blood and plasma. At all time points, samples for [¹⁴C]-radioactivity in whole blood and plasma will be taken. Samples for PK assessment of cold BI 1358894 will be collected for all PK samples taken and for its metabolites in plasma which will be collected at the metabolite PK time points in the [Flow Chart](#), after intake of radiolabelled drug on Day 1. PK sampling for the metabolites will continue as long as radioactivity in plasma is above LLOQ (< 30 dpm/mL)
3. The time is approximate; the procedure is to be performed within a time window of 3 h prior to drug administration.
4. All stools (for [¹⁴C]-radioactivity assessment [REDACTED]) will be collected quantitatively from Day 1 in sampling intervals as defined in the [Flow Chart](#) after intake of [¹⁴C] BI 1358894. Thereafter, if warranted, 24 h collections are to be performed on days 21-22, 28-29, 35-36, 42-43, and 49-50. A blank sample will be collected before drug administration on Day 1. Collection of the predose faeces sample will start from approximately -48 h before drug administration. Faeces sampling for [¹⁴C]-radioactivity assessment will be stopped when the release criteria for radioactivity recovery (Section 3.1) have been met (earliest stopping on day 15). “+” means end of last collection interval, start of following collection interval. All samples: planned for determination of [¹⁴C]-radioactivity.

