5. Urine collection intervals (for PK/[¹⁴C]-radioactivity assessment [REDACTED] (planned time): on Day -1 or Day 1 predose (blank) sample, on Day 1 prior to start of urine collection voiding of the bladder, and at the intervals defined in the [Flow Chart](#) up to 336 h after drug administration. Thereafter, if warranted, 24 h collections are to be performed on days 21-22, 28-29, 35-36, 42-43, and 49-50. Urine sampling for PK will be stopped when release criteria for radioactivity recovery (Section 3.1) have been met (earliest stopping on day 15). “+” means end of last collection interval, start of following collection interval. All samples: planned for determination of [¹⁴C]-radioactivity, BI 1358894 and its metabolites. [REDACTED]
6. If several actions are indicated at the same time point, the intake of meals will be the last action.

Proprietary confidential information © 2020 Boehringer Ingelheim International GmbH or one or more of its affiliated companies

7. End-of-trial (EOT) examination to be performed within 1 to 7 days after last discharge from the study centre, or, if all once-weekly 24 h sampling periods are needed, prior to discharge on Day 50. EOT examination includes physical examination, vital signs, ECG, safety laboratory, recording of AEs and concomitant therapies, neurological examination and suicidality assessment (C-SSRS).
8. Subjects are to be fasted for at least 10 h before sample is taken.
9. Blood sampling for an individual subject can be stopped if [¹⁴C]-radioactivity in plasma is below limit of detection (<LLOQ 30 dpm/mL) at two consecutive sampling time points for this subject.
10. The planned times for admission, discharge, start and end of the urine and faeces collection intervals are approximate. The procedures are to be performed within a time window of \pm 4 h to the planned time.
11. Subjects are to collect faeces at home within 24 h intervals before admission to once-weekly in-house collection intervals. Home collection intervals: Day 20-21, 27-28, 34-35, 41-42, and 48-49. If faeces are collected in the subsequent in-house collection interval, faeces collected at home will be discarded. If no faeces is collected in the subsequent in-house collection interval (no defecation), faeces collected at home will be used instead for analysis.
12. For definition of the individual subject's end of trial see Section [6.2.3](#)
13. Urine drug and alcohol screening will be done at this time point.

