2.1.3 Secondary endpoints

Part 1:

The following pharmacokinetic parameters will be determined for total [¹⁴C] BI 1358894 and BI 1358894 after single dose administration:

- AUC_{0-tz} (area under the concentration-time curve of the analyte in plasma over the time interval from 0 to the last quantifiable data point)
- C_{max} (maximum measured concentration of the analyte in plasma)

[figure not shown]
Part 2:

The following pharmacokinetic parameters will be determined for BI 1358894:

[figure not shown]
- AUC_{0-24} (area under the concentration-time curve of the analyte in plasma over the time interval from 0 to 24)
- C_{max} (maximum measured concentration of the analyte in plasma)
- $AUC_{\tau,ss}$ (area under the concentration-time curve of the analyte in plasma at steady state over a uniform dosing interval τ)

Proprietary confidential information © 2020 Boehringer Ingelheim International GmbH or one or more of its affiliated companies

- $C_{\max,ss}$ (maximum measured concentration of the analyte in plasma at steady state over a uniform dosing interval τ)

Proprietary confidential information © 2020 Boehringer Ingelheim International GmbH or one or more of its affiliated companies

Proprietary confidential information © 2020 Boehringer Ingelheim International GmbH or one or more of its affiliated companies

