3. DESCRIPTION OF DESIGN AND TRIAL POPULATION

3.1 OVERALL TRIAL DESIGN AND PLAN

The study will be performed as an open-label, single arm and single- or multiple dose trial in healthy male subjects in order to investigate the basic pharmacokinetics of BI 1358894, [¹⁴C]-radioactivity, including mass balance, excretion pathways and metabolism following a single oral dose of [¹⁴C] BI 1358894 in Part 1 and to investigate the pharmacokinetics of BI 1358894 and its metabolite(s) following multiple oral doses of 100 mg BI 1358894 administered as film-coated tablets in Part 2.

Part 1:

The planned radioactive dose per subject is 3.7 MBq (100 µCi). The [¹⁴C] labelled drug will be administered on Day 1. Subjects will remain at the study site from admission on Day – 1 up to discharge on Day 15 following the fulfilment of release criteria. Subjects will then be readmitted to the study centre for 24 h collection intervals of urine and faeces on Days 21, 28, 35, 42 and 49, if release criteria have not been met. Within 24 h before each of these once weekly in-house collection intervals, subjects are to collect faeces at home. This 24-h interval home collection faeces will be used for analysis in case no defecation occurs in the subsequent 24 h in-house collection interval.

For determination of whether release criteria have been reached for individual subjects, [¹⁴C]-radioactivity will be measured in excreta (urine and faeces). The actual recovery results will be reported as a percentage of the administered dose.

If one of the following release criteria is true (i.e., release criteria have been met), 24 h collection intervals after Day 15 will not be performed any longer/will be stopped:

- Greater than or equal to 90% of the administered dose has been recovered in urine and faeces combined over the investigational period, or
- If <1% of the dose administered has been collected in urine and faeces within 2 separate, consecutive 24 h intervals, and
- Concentration of total radioactivity in plasma <5% of C_{max} of total radioactivity in plasma

If the mass balance recovery is less than 90% on Day 15, subjects will still be asked to return to the clinic for 24 h collection of urine and faeces on Days 21, 28, 35, 42 and 49 or until the recovery is deemed to be sufficient for mass balance purposes. If a subject is unable to attend one of these visits, they may be allowed to reschedule the visit if needed.

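### Part 1's optional stop to blood sampling is triggered by the radioassay limit, and it can decide where parent AUC0-tz, a secondary endpoint, is cut off

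*Protocol*

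**What the plan says.** Protocol 5.3.2.1 has a paragraph on premature stopping. The trigger is plasma [14C]-radioactivity below the 30 dpm/mL quantification limit at two consecutive time points, after which "blood sampling can be stopped for this subject". The one restriction is: "However, all samples until 24 h after the last drug administration have to be taken". Part 1 Flow Chart footnote 9 gives the same trigger and opens "Blood sampling for an individual subject can be stopped if". Neither place separates radioactivity samples from parent samples.

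Parent has no schedule of its own. Part 1 footnote 2 says: "Samples for PK assessment of cold BI 1358894 will be collected for all PK samples taken". It ties metabolite sampling to radioactivity above the limit, but sets no such condition for parent. The Flow Chart plans blood samples to 336 h and at the weekly return visits.

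Protocol 2.1.3 and SAP 5.2.2 name AUC0-tz and Cmax, for total radioactivity and for BI 1358894, as the Part 1 secondary endpoints. AUC0-tz is taken "over the time interval from 0 to the last quantifiable data point". SAP 6.6, 7.4.1 and 7.5.2 refer PK handling to internal standards. The visible text has no rule for a tz set by stopped sampling and no common truncation time.

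**The concern.** For parent AUC0-tz, tz should be the last time at which parent itself can be quantified. Under the stopping rule it can instead be the time at which a different assay, measuring a different quantity, ran out of sensitivity. The stop is also optional, so two subjects with the same parent profile can end with different tz because sampling was stopped in one and not in the other. With 8 subjects in Part 1, that difference goes straight into the geometric mean and geometric CV planned in SAP section 7, and a reader of the table could not tell it from variation in exposure.

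**Working it through.** The documents give no figure for the effect of this rule, so there is none to reproduce.

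**1. The limit in mass units.** Inputs are from protocol 4.1.1 and 5.3.2.1. The dose figures agree with each other: 100 µCi × 0.037 = 3.7 MBq, and 10 mL × 10 mg/mL = 100 mg.
- Specific activity: 3.7 × 10⁶ Bq × 60 / 100 mg = 2.22 × 10⁸ dpm / 100 mg = 2,220 dpm/µg.
- Limit: 30 / 2,220 µg/mL = 13.5 ng-eq/mL.
- Molecular weight is not given. At an assumed 300, 400 or 600 g/mol, the limit is 45, 34 or 23 nM-eq.

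Total radioactivity includes parent, so parent is at most about 13.5 ng/mL when the rule triggers. What can be lost is the tail below that level.

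**2. How much AUC the 24 h floor leaves unprotected.** Protocol 1.2.1 reports an accumulation ratio of 2.5 on AUC0-24 (10 and 25 mg). With linear kinetics, AUC0-24 / AUC0-∞ = 1/2.5 = 40%, so about 60% of parent AUC0-∞ lies after 24 h.

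**3. Whether parent is measurable below the radioassay limit.** No parent LLOQ is visible. Protocol 1.2.1 reports sampling to 672 h after 200 mg fed, a late half-life of about 200 h, AUC0-24 of 11,640 nM·h, and less than 20% of AUC beyond 192 h. Taking the 2.5 ratio:
- AUC0-∞ ≈ 2.5 × 11,640 = 29,100 nM·h.
- C at 192 h ≤ 0.20 × 29,100 × ln 2 / 200 = 20.2 nM.
- C at 672 h ≤ 20.2 × 2^(−480/200) = 3.8 nM.

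That is about 6 to 12 times below the limit (23/3.8 to 45/3.8). This is an inference from an earlier trial, not a stated assay property.

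**4. Illustrative size.** Tablet AUC0-24 at 200 mg fasted is 11,640 / 2.4 = 4,850 nM·h. A less-than-proportional dose response puts 100 mg fasted between 2,425 and 4,850. Part 1 gives an oral solution, for which no exposure is stated, so up to 2.5 times those values was also tried. The assumed profile has 60% of AUC after 24 h, later phases of 40 h and 200 h, and 12% of AUC beyond 192 h. About 6.1% then lies beyond 336 h. The rule was applied at the Part 1 sampling times, with the stop taking effect at the second value below the limit.

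Loss of AUC to 336 h = (share after stop − 6.1) / (100 − 6.1).

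| AUC0-24 (nM·h) | MW (g/mol) | Total / parent | Stop (h) | Parent at stop (nM) | AUC0-∞ after stop | Loss of AUC to 336 h |
|---|---|---|---|---|---|---|
| 2,425 | 300 | 1 | 48 | 32.9 | 44.1% | 40% |
| 2,425 | 400 | 1 | 72 | 22.6 | 33.2% | 29% |
| 2,425 | 400 | 2 | 120 | 11.1 | 20.5% | 15% |
| 4,850 | 400 | 1 | 120 | 22.2 | 20.5% | 15% |
| 2,425 | 400 | 4 | 192 | 4.5 | 12.0% | 6% |
| 4,850 | 400 | 4 | 288 | 3.8 | 7.4% | 1% |
| 12,125 | 400 | 4 | 485 | 3.8 | 3.5% | none |

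The large losses need parent to be all of the plasma radioactivity at the lowest exposure. A delay in reporting radioactivity results, for which the documents give no figure, would move the stop later and shrink every loss.

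**The case against.** The case against has real weight. The stop is optional and needs two consecutive low values. The mandatory 24 h protects Cmax: protocol 1.2.1 puts the tablet peak at 1 to 5 h. AUC0-tz is by definition exposure to a last quantifiable point, so tz varies between subjects in any case, and it is not an estimate of AUC0-∞. The endpoint is secondary and descriptive. LC-MS is named only for Part 2 (protocol 3.2), and Part 1 assay text may be redacted. All of this stands. It limits the size and the certainty, but it does not alter the fact that the rule covers parent samples.

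Three stronger readings are tempting, and the documents do not support them.
- *That the same limit undermines the plasma release criterion in 3.1.* A level of 5% of Cmax can be resolved only if total-radioactivity Cmax is at least 13.5 / 0.05 = 270 ng-eq/mL. Below that, the criterion is simply not shown to be met and collection continues, which is conservative for recovery. The criterion is also joined to the excreta criterion, and 90% recovery is a separate route. Rewording it to accept values below LLOQ would loosen release.
- *That the design says it needs the plasma tail.* Section 3.2 ties multiphasic elimination to prolonged excreta collection. Longer-term parent PK is assigned to Part 2, which samples to Day 62.
- *That the protocol's figures bound Part 1 parent Cmax.* They come from tablets, not from the oral solution.

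**Conclusion.** The point holds as a gap in wording. As written, a stop triggered by the radioassay can fix tz for parent AUC0-tz, at different times in different subjects and for reasons unrelated to parent. This follows from the text and needs no modelling; it matters only if parent is still quantifiable at the trigger, which is likely from step 3 but inferred. The conversion to 13.5 ng-eq/mL is exact on the stated dose. The size is not: it runs from none, if radioactivity stays above the limit to 336 h, to about a third of parent AUC to 336 h, with 40% in the most extreme case tried. The range rests on assumed molecular weight, parent share of radioactivity, solution exposure and profile shape. Cmax and the primary recovery endpoints are outside this point.

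**What to change.** In protocol 5.3.2.1 and Part 1 Flow Chart footnote 9, limit the stop to radioactivity and metabolite samples. State that the scheduled BI 1358894 plasma samples continue to 336 h, or until parent is below its own LLOQ at two consecutive times.

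The cost is a change of wording plus a few small draws and assay runs in subjects who would otherwise have stopped. All fall at times already in the Flow Chart, while subjects are in-house to Day 15, so the planned schedule does not grow. If sampling can no longer be changed, the report should list tz for each subject and whether the stop was used.
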